### **IDI guide for community led distributors**

Thank you for taking time to speak with me today. My name is \_\_\_\_\_ and I am working with Zambart a research organization. In order to increase the uptake of HIV services, HIV self – testing kits are being distributed in the community (tuntemba). We would like to hear what you think about this as well as what the community thinks. We will record the interview in order to make sure that we capture all of the valuable information that you share with me. We will also be taking down notes so that I do not forget what we have discussed. Please feel free to give honest answers as what we say is confidential. We will not record your name on the tape or on the notes that will be written and no one else will see the tape or the notes besides people who are working on this research project.

#### **A. HIV-Self testing**

1. What is your understanding of HIV self-testing?
  - a. Definition
  - b. Procedures
    - i. Processes for sample collection, analysis, and interpretation of results
  - c. Do you feel you have good understanding of all aspects related to self-testing?
    - i. What is the source of your current knowledge on self-testing?
    - ii. In what instances are confirmatory tests required?
    - iii. What sort of information/training would you need to better support self-testing patients/participants?

#### **B. Evaluating the model**

1. What do you think about (community-led, ANC, PLWHIV, Tuntemba) distribution of HIV self-test kits?
  - i. Is it a good/bad thing? Please explain
  - ii. How can it be made better?
  - iii. How would you prefer that self-test kits are distributed?
- b. What impact has self-testing had in the communities that you serve?
  - i. Positive impact? Please explain
  - ii. Negative impact? Please explain
2. What are the barriers and facilitators to self-testing
  - a. From the points of view of health care workers like yourself
  - b. From the community/clients' perspectives?
3. What are your views on the community led distribution self-testing model?
  - a. Will it increase uptake of HIV testing (compared to provider-delivered testing)?
    - iv. What sorts of people are using this self-testing service?
    - v. What type of people are not using the service and why?

**C. Linkage to care**

1. What are your views on linkage to prevention and care services after self-testing? Do you think people will link as well, or better, or worse than if they were tested by providers?
  - a. Linkage to medical male circumcision for HIV negative males
  - b. Linkage to HIV treatment/care for those who test HIV positive
  - c. What is your role in linking people to care and preventive services?
  - d. What are the barriers to linking to care in this model?
  - e. What are the facilitators to linking to care?

**D. Social harms**

1. What are your views on social harms due to self-testing?
  - a. Do you think self-testing will have higher rates of social harms compared to provider-delivered testing? What sorts of harms do you think could result?
    - i. Forced testing?
    - ii. Gender based violence?
  - b. Have you experienced any harm as a result of distributing kits to clients?
  - c. Are there any unfavourable outcomes as a result of people collecting kits for their partners in this community?

**E. Sustainability**

1. How can we sustain the giving of kits through ANC, PLWHIV, and Shops?
2. How can the community help in sustaining the different ways of distributing the kits?
3. What are the factors in the community that may cause these ways of distribution to be unsuccessful?
4. What do you think can be done to motivate the distributors?
5. What do you think are the demotivating factors?

Do you have any questions or are there other things which are related to this topic that you would like to talk about?

## **IDI (community led models)**

Thank you for taking time to speak with me today. My name is \_\_\_\_\_ and I am working with Zambart a research organization. In order to increase the uptake of HIV services, HIV self – testing kits are being distributed at the ARTs clinic and ANC. We would like to hear what you think about this as well as what the community thinks. We will record the interview in order to make sure that we capture all of the valuable information that you share with me. We will also be taking down notes so that I do not forget what we have discussed. Please feel free to give honest answers as what we say is confidential. We will not record your name on the tape or on the notes that will be written and no one else will see the tape or the notes besides people who are working on this research project.

### **A. General information**

1. (record sex of participant):
2. What year were you born?
3. Where do you live- zone/ section of the community?
4. What is your marital status?
5. How far did you go in your education?
6. What is your religion?

### **B. Knowledge of HIV/ HIVST and attitudes towards testing for HIV?**

1. What methods of HIV testing do you know?
2. What are the advantages and disadvantages of testing for HIV using this/ these method (s)?
3. How often do you test for HIV and why? It usually takes a long time/ a short time before you test, why? (probing for attitudes)
4. How often do you come to access HIV services and why?

### **C. Location and lay-out of distribution points, including community social and physical features**

1. What do you like about the location of the kantemba/hub distribution point? (probe)
2. What didn't you like about the location of distribution kantemba/hub point? (probe)
3. How did the location improve or hinder your access of HIVST services? (probe)
4. How did the location influence your decision to accept or reject HIVST? (probe)
5. What could be done to improve this service?

#### **D. Linkage to care**

1. How easy or difficult do you think it is to have a confirmatory test done? Probe: availability of testing services, location of testing services, stigma, attitude of HCWs,
2. (For those who are negative) How easy or difficult was it to access prevention services- condoms, VMMC, PMTCT (for those who tested negative and are willing to share experience)
3. Do you know anyone who has started treatment as a result of kantemba/ community hub distribution?
4. (**For those who have started treatment**) What factors may have facilitated their decision to start treatment? Probe:
5. (**For those who have not started treatment**) What factors may have hindered their decision to start treatment? Probe:
6. In your opinion, what are the other barrier of linkage to confirmatory testing and care?
7. What can be done to help people who access kits through the community hubs link to care?
8. Do you have anything to add?

We have come to the end of our interview, thank you very much for your time.

## **IDI work place model**

Thank you for taking time to speak with me today. My name is \_\_\_\_\_ and I am working with Zambart a research organization. In order to increase the uptake of HIV services, HIV self – testing kits are being distributed at work places. We would like to hear what you think about this as well as what the community thinks. We will record the interview in order to make sure that we capture all of the valuable information that you share with me. We will also be taking down notes so that I do not forget what we have discussed. Please feel free to give honest answers as what we say is confidential. We will not record your name on the tape or on the notes that will be written and no one else will see the tape or the notes besides people who are working on this research project.

### **A. General information**

1. (record sex of participant):
2. What year were you born?
3. Where do you live- zone/ section of the community?
4. What is your marital status?
5. How far did you go in your education?
6. What is your position

### **B. Knowledge of HIV/ HIVST and attitudes towards testing for HIV?**

1. What methods of HIV testing do you know?
2. What are the advantages and disadvantages of testing for HIV using this/ these method (s)?
3. How often do you test for HIV and why? It usually takes a long time/ a short time before you test, why? (probing for attitudes)

### **C. Location and lay-out of distribution points, including community social and physical features**

1. What do you like about the location of the workplace distribution point? (probe)
2. What didn't you like about the location of the work place distribution point? (probe)
3. How did the location improve or hinder your access of HIVST services? (probe)
4. How did the location (within the work place) influence your decision to accept or reject HIVST? (probe)
5. What could be done to improve this service?

### **D. Power and social relations**

1. How did what society believe in influence your decision? What beliefs/ issues influenced your decision?

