#### **1.4 Studies of HIVST distribution in Zambia**

In addition to clinical performance studies, three cluster-randomised trials of community-based distribution have been conducted in Zambia. In one trial, conducted in four urban communities, we found that the door-to-door offer of HIVST as an option for HIV testing by lay counsellors, which included the option for individuals to take an HIVST for secondary distribution, reached men and younger adults.[15] The second trial, a cluster randomised trial of community-based distribution of HIVST is ongoing as part of STAR Phase I. A third trial among female sex workers, using peer educators and their clients as the unit of randomization, found that HIVST was acceptable, but did not address gaps in the care cascade among a population with high levels of HIV testing and linkage to care overall [16]. Findings arising from the completed HIVST trials, and other studies of HIVST in the region, have led to HIVST being adopted as a routine service delivery through health facilities in Zambia.

There remains, however, a need to understand the relative costs, benefits and harms associated with different models of delivery; whether different models of HIVST distribution are feasible, reach individuals, particularly men, previously unaware of their HIV status; and link individuals to HIV prevention or care services. In particular, there is a need for evidence of less labour-intensive and costly models of HIVST distribution. Numerous models of HISVT distribution are being tried in different settings. How these models are implemented in practice, how different models of distribution are experienced by intended users, and whether these models reach population subgroups underserved by available HTS all need to be understood to support decision-making around resource allocation for HIVST.

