### **2.2 Study objectives**

For each of the five distribution models, the specific objectives are to use routinely collect programmatic data and qualitative data from the case studies to:

1. Describe, quantitatively, the process of distributing HIVST kits through each of the five distribution models;
2. Understand individuals' experiences of the different models of HIVST distribution;
3. Explore contextual factors likely to influence the acceptability of different models of HIVST to direct and secondary-distribution kit recipients. For example, at community level we will explore how availability of alternative HTS, anticipated and enacted stigma, and location of the distribution models influence people's choices. At interpersonal level, we will explore how power dynamics within a couple influence individuals' decisions.

4. Evaluate the frequency and nature of social harms associated with distribution of HIVST kits, and
5. Develop generalizable qualitative tools that can be used to evaluate different distribution models among key target populations

For four of the five models (all models except VMMC) we will also measure:

6. Costs, from the patient and the provider-perspective, of accessing and delivering HIVST kits, and those relating to linkage into confirmatory testing and care for individuals who self-test HIV-positive
7. The incremental cost-effectiveness of additional HIVST distribution models
8. Patient costs and their willingness-to-pay for HIVST

For the two secondary distribution models (implemented in ANC and HIV testing and treatment services), we will recruit a cohort (Secondary Distribution cohort) of index patients and their sexual partners (intended users of the HIVST kit) in order to investigate:

9. Factors associated with acceptance of HIVST for secondary distribution to index patients, with acceptance evidenced by accepting an HIVST kit(s) for onward secondary distribution.
10. Factors associated with the successful secondary distribution of HIVST to the sexual partners (the intended users of the secondary distribution HIVST kits) of index patients, as evidenced by the proportion of index patients who report that their primary partners used the HIVST kit within approximately 1-month of distribution
11. The proportion of intended users of the secondary distribution HIVST kit who report having accessed confirmatory testing, or HIV prevention or care services within approximately 3-months of distribution

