## **4.2 Qualitative methods**

Qualitative data collection will begin with implementation of participatory activities through community consultation processes and stakeholder discussion, followed by IDI, FGD, mapping, and observation of HIVST distribution (Table 2). Qualitative data will provide understanding of contextual factors that mediated people's choices and behaviour. The qualitative research will explore the following themes:

1. Social support and social networks (friends, workmates, church, customs, support after testing, attitudes of HCWs)
2. Livelihood options
3. Knowledge of HIV testing and HIVST, and individual attitudes towards HIV testing and HIVST
4. Power relations, social harms and gender-based violence within couple/partners
5. Social effects of HIVST including stigma
6. Location and lay-out of distribution points, including community social and physical features
7. Environmental factors (flooding, disease outbreaks, strikes etc.)
8. Promotion and social marketing

A total of 12 FGDs and 46 IDIs will be conducted (see table 2 for distribution). Both the FGDs and IDIs will be conducted by trained RAs with the help of a Junior and senior social scientist. The Neighbourhood Committee (NHC) members will help to identify appropriate venues within the community. The NHC is a community-based organisation created by an act of parliament to ensure community involvement in the management of health related programmes in the community. The size of the focus groups will be between 8-12 participants. This is the recommended size to ensure interaction between the participants. Focus group discussion and IDI participants will be selected purposively for each distribution model, aiming for a range of ages, men and women, and individuals who accepted or declined an offer of HIVST. The composition of the FGDs is described in section 5.1 (recruitment of qualitative study participants). In addition 4 stakeholder discussions with representatives of community based groups and 15 observations of the mechanisms of distribution and interactions between distributors and clients will be conducted.

Twelve individuals from each of the quantitative cohorts linked to secondary distribution methods (24 in total) will be purposely selected to take part in the Secondary Distribution qualitative cohort. They will be interviewed at two points: at recruitment and follow-up.

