### **7.1 Qualitative data analysis**

In-depth interviews and FGD will be audio-recorded. Qualitative RAs will play the recordings and transcribe the recording. A draft codebook will be developed earlier, before fieldwork using the objectives of the qualitative enquiry. It will be reviewed during field work and transcription to take into account emerging issues. The initial codebook will be developed with reference to the contextual factors which the study will be exploring and later reviewed for the emerging issues from the IDIs, FGDs, and field notes. As the particular design used for this study is not grounded theory, no attempt will be done to conduct a constant comparative analysis to reach saturation. However, having extended contacts with participants and tools with scripted probes will help to generate detailed and rich experiences by the participants. Qualitative RAs will transcribe the interviews straight onto special designed matrices. These matrices will contain thematic areas found in the codebook which will have been reviewed at this stage. This will enable the interpretation and comparison of the findings within specific thematic areas as well as across themes, participants, and distribution models. In the long term, all interviews will be fully transcribed by re-listening to the recordings, imported into Nvivo or Atlas ti and coded using a revised codebook.

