### **10.2 Potential harms and/or risks**

HIV testing, including HIVST, is well established and known to have a high level of safety [13]. However, harmful reactions can occur. Adverse events (AE) related to HIVST include all undesirable experiences that result directly from use of the HIVST kit itself or as a reaction from others due to the presence of the kit, use of the kit or results produced from the kit. AEs can be from one person to another, or a person to themselves, and can occur before, during or after self-testing. HIVST may pose harms distinct from HTS performed by a healthcare worker, including concerns of coercion to test. The research described above explores the experiences of clients receiving HIVST through both primary and secondary distribution models, and each of these has potential risks for clients and test users.

Most previous research assessing HIVST has focused on primary distribution models, in which the intended HIVST user receives a test kit from a healthcare worker or lay provider. Studies of primary distribution models have shown that the models are acceptable and safe for clients, with few or no social harms reported. To date, studies of the distribution of HIVST by volunteer-counsellors in Malawi have found a low incidence of harms. Some 3% of individuals reported feeling coerced into self-testing, however, among this group of individuals, 92% were highly satisfied with self-testing and 94% stated they would recommend self-testing to family/friends. We found little evidence of serious adverse events due to HIVST in a 3ie-

funded trial of the door-to-door offer of HIVST as an option for HIV testing and a STAR-funded trial of the impact of community-based self-test distribution on population testing coverage.

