## **H. Social harms**

1. After delivering the test kit to your partner, did you experience any problems?
2. Please describe any kind of problems you faced? For example: beaten, yelled at, denied sex, marriage break-up, not given money, being locked out, being neglected, or being threatened.
3. What do you think made your partner respond to you in such a way?

What is it that you think we can do to prevent such problems from happening again in the future (probe: can home based counselling work,

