**D. Linkage to care**

1. How easy or difficult do you think it is to have a confirmatory test done? Probe: availability of testing services, location of testing services, stigma, attitude of HCWs,
2. (For those who are negative) How easy or difficult was it to access prevention services- condoms, VMMC, PMTCT (for those who tested negative and are willing to share experience)
3. Do you know anyone who has started treatment as a result of kantemba/ community hub distribution?
  - a. **(For those who have started treatment)** What factors may have facilitated their decision to start treatment? Probe:
  - b. **(For those who have not started treatment)** What factors may have hindered their decision to start treatment? Probe:
4. In your opinion, what are the other barrier of linkage to confirmatory testing and care?
5. What can be done to help people who access kits through the community hubs link to care?
6. Do you have anything to add?

We have come to the end of our interview, thank you very much for your time.

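### Social harms are ascertained by unequal methods across the five models, and the one-to-one user guides for the community-led and workplace models omit the theme altogether

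*Protocol*

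**What the plan says.** Section 2.2 states objective 4, to "Evaluate the frequency and nature of social harms associated with distribution of HIVST kits", for each of the five models, using programme data and qualitative data. The Summary says that the qualitative methods, in-depth interviews included, will also document how social harms arise and are managed. Section 4.2 lists as a theme "Power relations, social harms and gender-based violence within couple/partners". Section 7.1 relies on scripted probes and transcription onto theme matrices, so as to allow "comparison of the findings within specific thematic areas as well as across themes, participants, and distribution models".

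Appendix 4 holds the guides. The first index interview in the secondary-distribution cohorts has a harm section that opens with "After delivering the test kit to your partner, did you experience any problems". The community-led user guide, printed twice, covers general information, knowledge, location and linkage. Its linkage section asks "What can be done to help people who access kits through the community hubs link to care" and then only whether the participant has anything to add. The workplace user guide ends with "How did what society believe in influence your decision? What beliefs/ issues influenced your decision".

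Section 5.1 provides community-based mechanisms for identifying and documenting harms in all models except the two secondary-distribution ones. Their form depends on the consultations. In the two excepted models, qualitative participants are to be interviewed about harms instead.

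**The concern.** An objective that covers five models needs some means in each model by which a user can report harm. In models 2 and 3 the person who took the kit is not asked in the one setting suited to the question, a private interview. The matrix cells for harm in those interviews would fill only with what participants volunteer, and someone reading across models could take an empty cell as a finding.

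What is at stake is the reading of safety when the results inform scale-up. Section 1.4 gives, as part of the motivation, the need to understand the "relative costs, benefits and harms associated with different models of delivery". Coercion is the clearest case. Section 10.2 names it as a concern distinct to self-testing and reports from earlier work in Malawi that "Some 3% of individuals reported feeling coerced into self-testing". The grading table in Appendix 4 puts coercion to self-test or to disclose a result at Grade 2. In models 2 and 3 pressure need not come from a partner: facility-led clients show used kits to staff (Appendix 1), and workplace kits are handed out on the employer's premises (section 3).

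**Working it through.** The protocol states no figure on this point, so the check is a reading of each tool by model, followed by a small illustration of what the numbers asked could show.

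**1. Harm capture by model**

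| Model | Harm questions put one-to-one to users | Other channels |
|---|---|---|
| 1 VMMC | No guide headed for VMMC clients in Appendix 4 | Community mechanism (5.1) |
| 2 Facility- and community-led | None in either copy of the community-led guide; no guide is headed facility-led | Community mechanism; section F of the community-led group guide, limited to kits passed between partners; distributor and health-worker interviews |
| 3 Workplace | None | Community mechanism, if it reaches the site; the community-led group guide mentions work places in its section C, but which guide the workplace group uses is not stated |
| 4 and 5 Secondary distribution | Index questionnaire at one month: 7 harm items (SHS_Fu_3a to 3g) and 2 attribution items (4a, 4b); first and second interviews with index and partner; a forced-testing item in the partner questionnaire | Group discussion section G; health-worker interviews; excepted from the mechanism in 5.1 |

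**2. Programme data do not fill the gap.** The process data listed in section 4.3.1 are demographics, acceptance and reasons for refusal. The workplace questionnaire in Appendix 6 has no harm item. The columns of the facility- and community-led register cannot be seen in the text at hand.

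**3. Workplaces.** Section 4.1 says the workplaces may not be in the five communities, so a mechanism built on those communities may not reach them. The workplace observation tool has no harm item either.

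**4. What the numbers could show.** Section 5.1 plans 6 user interviews for the facility- and community-led model and 6 for workplaces. Section 5.4 plans 450 index patients per secondary cohort with up to 30% lost, so 450 × 0.70 = 315 would be asked the harm items. Let r be an assumed true rate of any reportable harm. The protocol gives no such rate, so a range is shown. The 3% coercion figure is not used as r, because the seven index items do not ask about coercion to test.

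- Chance of at least one report among n people asked: 1 − (1 − r)^n. Expected reports: n × r.

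| r | n = 6: chance, expected | n = 315: chance, expected |
|---|---|---|
| 1% | 5.9%, 0.06 | 95.8%, 3.15 |
| 3% | 16.7%, 0.18 | >99.9%, 9.45 |
| 5% | 26.5%, 0.30 | >99.9%, 15.75 |

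- Exact one-sided 95% upper bound after zero reports: 1 − 0.05^(1/n). For n = 6 it is 39%; for n = 315 it is 0.9%.

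Even with a harm question added, six interviews with no report are compatible with a true rate as high as 39%. The added question would therefore inform the nature of harm, not its frequency.

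**The case against.** The strongest reply is that the protocol deliberately uses different channels. Section 5.1 gives models 1 to 3 a community mechanism and sets interviews about harm against it for models 4 and 5. Sections 8.4 and 10.2 add a reporting system, neighbourhood health committee meetings and police victim-support contacts, and the appendices supply report forms. The community-led group guide and both provider guides have harm sections. Closer questioning in secondary distribution is also proportionate: section 10.2 says evidence there is thinner and the risks may be serious, while primary distribution has shown few or no harms. Finally, the theme in section 4.2 is worded around couples, so pressure from an employer or shop owner goes beyond its letter.

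Much of this stands. A reader might infer that models 2 and 3 will look safe by construction, or that the bias runs against secondary distribution. The documents do not support either reading: models 1 to 3 have a channel that section 5.1 withholds from models 4 and 5, and the net direction cannot be known. Nor does the protocol define a formal comparison of harm rates. Section 7.1 describes a general thematic comparison, and section 1.4 is background. A contrast of reports expected from the cohorts with none from these interviews would mostly reflect 315 people against 6.

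It does not remove the gap. The mechanism is not yet designed and may not reach workplaces. Providers can be the source of pressure. The group prompt is confined to kits passed between partners and is answered before others. Objective 4 is not limited to couples, and the two user guides omit even the couple-based version of the theme.

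**Conclusion.** The point holds in a limited form. Harm is ascertained by different and unequal methods across the five models, and two one-to-one user guides leave out a theme that sections 2.2 and 4.2 commit the study to. No report of harm in those interviews is not evidence of no harm. Up to 12 planned interviews are affected (6 + 6). The figure is an upper limit, because section 5.1 does not say how the six facility- and community-led interviews divide or which guide facility-led users receive. The case is strongest for the workplace model.

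The conclusion rests on the guides being used as printed; an interviewer may probe beyond them, and section 7.1 lets the codebook grow with emerging issues. It does not depend on any harm rate: the 1% to 5% range serves only to show that interviews in these numbers cannot supply a frequency. The change should be made, but nothing here undermines the cohorts' primary outcome.

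**What to change.** - **Appendix 4.** Add a short harm and coercion section to both copies of the community-led user guide, to the workplace user guide, and to whatever guide is used for VMMC and facility-led clients. Word it for people who took a kit for themselves: problems after collecting, keeping or using it; pressure from a distributor, employer, peer or partner to take it, test or disclose; who was involved and what followed.
- **Section 7.1.** State that harm capture differs by model, as section 5.1 sets out. State that questionnaire-based frequencies from models 4 and 5 are reported separately and are not comparable with models 1 to 3, and that cross-model statements on harm are limited to questions asked in every model.

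The cost is a few questions in guides that section 8.1 already requires to be translated, and a sentence or two in section 7.1. The downside is a slightly longer interview, perhaps 5 minutes (an assumption) on the 30 to 45 minutes planned for workplace participants. No change to sample size is needed.
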